#### **5.5.1.2 Sensitivity analyses**

Several sensitivity analyses will be performed for the final analysis of the primary endpoint.

In the first, the main analysis will be repeated using the dataset from multiple imputation of the missing data in the ITT Set, to compare treatment groups using the PPS.

In the second, the analysis will be performed using a Mixed Effects Model with Repeated Measures (MMRM) with an unstructured covariance matrix, where the treatment group, time (as a categorical variable), treatment by time interaction, and patient age at screening will be included in the model as fixed effects; patient will be a random effect; baseline HFMSE and baseline by time interaction will be included as a covariate. No imputation for missing visit data will be performed and the analysis will be performed on the ITT Set.

In the third sensitivity analysis, only the subset of subjects in the ITT Set who have non-missing values at 15 months will be analyzed using the same ANCOVA model as for the main analysis, in essence an analysis of ‘completers’.

In the fourth sensitivity analysis the missing Month 15 values will be imputed by ‘last observation carried forward’. This will be performed on the ITT set and data will be analyzed by analysis of covariance with treatment group as the factor and subject age at screening and baseline value as covariates.

In the fifth sensitivity analysis the main analysis using multiple imputation will be repeated but for subjects who have a missing 15-month assessment and discontinue due to treatment failure or death the worst of the last observed value or the baseline value will be imputed.

The reasons for treatment termination are captured in the CRF in several categories as: ‘Investigator judgment’, ‘Voluntary withdrawal’, ‘Pregnancy’, ‘Ineligibility’, ‘Protocol deviation’, ‘Adverse Event’ or ‘Other’, and a free text field captures further detail. Therefore, a blinded medical review will be conducted, prior to unblinding to adjudicate if any are due to treatment failure. This list will then be used in determining a subject’s response.

From each imputation method, the data will be analyzed by analysis of covariance with treatment group as the factor and subject age at screening and baseline value as covariates.

#### **5.5.1.3 Exploratory analyses**

In order to further explore the change in HFMSE score during the study and the difference between treatment groups the change from baseline to each visit will be analyzed using an ANCOVA model and multiple imputation as described for the main analysis. A plot of mean

change from baseline (based on the estimates from the ANCOVA model) over time will be provided by treatment group.

The total HFMSE score and change from baseline to each visit will be presented using observed values. Individual items of the HFMSE and changes from baseline to each visit will be investigated to determine the pattern of shifts.

Graphical representations to show each individuals response and Forest plots to summarize the primary endpoint and corresponding sensitivity analyses may be presented.

Analyses will be conducted on the ITT Set and PPS.

### **5.5.2 Interim analysis of primary endpoint**

#### **5.5.2.1 Main analysis**

An interim analysis may take place as described in Section 5.1. At the interim analysis, the primary endpoint will be analyzed using the same ANCOVA model as planned for the final analysis. Endpoint values will not be available for many of the subjects at the interim analysis and the approach to handling missing post-baseline HFMSE data will also be the same as for the final analysis using the multiple imputation method (Section 5.3).

Analyses will be conducted on the ITT Set.

#### **5.5.2.2 Sensitivity analyses**

The sensitivity analyses planned for the final analysis of the primary endpoint will be repeated at the interim with the exception of the PPS analysis.

The analysis of subjects with non-missing Month 15 values described for the primary endpoint will be performed at 15 months, but it is noted that since this is an interim analysis the number of subjects available will be small so this is included to explore the trend.

One exploratory analysis using the same ANCOVA model as the primary analysis may be performed based upon the IES. In the event a subject is in the IES but has a missing value at 15 months then the median value for the subject at Month 15 across the 100 datasets from the multiply imputed data will be used in the imputation.

The exploratory analyses outlined in Section 5.5.1.3 will be performed at the interim on the ITT Set using the imputed dataset from the main analysis.

### 5.5.3 Summary of analyses of the primary endpoint

#### Summary of analyses for the primary endpoint

Analysis Method	Final Analysis - Population: further notes	Interim Analysis - Population: further notes
Main analysis		
Analysis of covariance (treatment as fixed effect) with subject's age at screening and baseline HFMSE value as covariates	ITT; multiple imputation used to impute missing 15-month values	ITT Set; multiple imputation used to impute missing 15-month values
Sensitivity analyses		
Analysis of covariance (treatment as fixed effect) with subject's age at screening and baseline HFMSE value as covariates	PPS; multiple imputation used to impute missing 15-month values	
MMRM model - treatment group, time (as a categorical covariate), treatment by time interaction, and patient age at screening will be included in the model as fixed effects; patient will be a random effect; baseline HFMSE and baseline HFMSE by time interaction will be included as a covariate.	ITT: no imputation	ITT Set, no imputation
Analysis of covariance (treatment as fixed effect) with subject's age at screening and baseline HFMSE value as covariates	Subset of ITT with non-missing 15-month values	ITT Set; with non-missing 15-month values
Analysis of covariance (treatment as fixed effect) with subject's age at screening and baseline HFMSE value as covariates	ITT; last observation carried forward used to impute missing 15-month values	ITT Set; last observation carried forward used to impute missing 15-month values
Analysis of covariance (treatment as fixed effect) with subject's age at screening and baseline HFMSE value as covariates	ITT Set with Multiple imputation; worst of the baseline and last observed value for subjects who discontinue due to treatment failure or death. If missing for any other reason then use value from MI	ITT Set with Multiple imputation; worst of the baseline and last observed value for subjects who discontinue due to treatment failure or death. If missing for any other reason then use values from MI.

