## **2 Study design**

This is a Phase 3, multicenter, double-blind, randomized, sham-procedure-controlled study of ISIS 396443 administered intrathecally over 15 months to patients with later-onset SMA. Approximately 117 subjects will be randomized 2:1 to receive a 12 mg dose of ISIS 396443 or undergo a sham procedure as control, respectively. Randomization will be stratified based on the subject's age at screening: <6 years versus  $\geq$ 6 years. A separate randomization list will be used for Japan. If a subject does not successfully receive the first dose of ISIS 396443 or undergo the first sham procedure, they will be replaced.

ISIS 396443 will be administered using a loading regimen (dosing on Study Days 1, 29, and 85) followed by a maintenance dosing 6 months thereafter (Day 274). Subjects randomized to the sham-procedure control group will undergo a sham-procedure on Study Days 1, 29, 85, and 274.

No adjustment of dose is permitted. However, should a concurrent illness prevent the dosing procedure from being performed safely, each scheduled dose may be delayed by up to 4 weeks.

The study will consist of screening, treatment, and post-treatment follow-up-periods. The total duration of participation in the study is approximately 16 months.

Blinded safety data will be reviewed on an ongoing basis by the Sponsor and the Medical Monitor. Unblinded safety data will also be reviewed on an ongoing basis by an independent Data Safety Monitoring Board (DSMB) (Section 6.6). In the protocol it was planned that an interim analysis may be conducted when all subjects will have completed the month 6 assessment and at least 39 will have completed the month 15 assessment. An interim efficacy analysis will be conducted using a targeted cut-off date of 31 August 2016 for the clinical data. At the time of the interim analysis, it is expected that approximately 52 subjects will have attended the Month 15 assessment and all 126 subjects will have had the opportunity to attend the assessment at Month 6 (Section 5.1).

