### 5.1 Interim and final efficacy analyses

An interim analysis may take place when all subjects have completed the 6-month assessment and at least 39 subjects have completed the 15-month assessment with a targeted clinical cut-off date of 31 August 2016. At the interim analysis, only the primary endpoint will be tested. The final efficacy analysis will take place when the last subject completes the 15-month assessment or earlier if the study is terminated on the grounds that conducting a sham-controlled study is no longer deemed ethical based on the assessment of risk-benefit of ISIS 396443.

At the interim analysis and final analysis, the same analysis of covariance (ANCOVA) model will be used in analyzing the change from baseline in HFMSE score to month 15. At the interim analysis, the month 15 endpoint values will not be available for some patients, so a multiple imputation method will be used to estimate them ([Section 5.3](#)). This method will also be used in the final analysis for the primary endpoint

The interim analysis results will be reviewed by an independent Data Safety Monitoring Board (DSMB) and an Unblinded Senior Management Team from the Sponsor. Recommendation will be made on whether it is appropriate for the trial to continue according to the current protocol or whether the protocol needs to be modified. During the interim analysis, subjects will continue in the study.

In the protocol it had been planned to conduct the interim efficacy analysis with an alpha of 0.02, however in finalizing this statistical analysis plan it was decided to conduct the interim analysis at a significance level of 0.025. If the study is not stopped at the interim analysis, the final analysis (test and confidence interval estimate procedures) will be conducted at a significance level determined by the resampling procedure as follows.

Let  $T_1$  and  $T_2$  be the standardized test statistics at the interim and final analyses, respectively. In order to determine the alpha level for the final analysis, the correlation between  $T_1$  and  $T_2$  is first estimated based on the resampling approach (Westfall and Young 1993):

- Among the 126 subjects enrolled in the study, randomly assign 84 subjects to the ISIS 396443 group and 42 subjects to the sham control group.
- Apply the re-randomized treatment assignment to the interim data and obtain the standardized test statistics  $T_1$ .

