## **5.9 Unblinding Plan for the Interim Analysis**

The interim analysis will be performed by a contract research organization (Parexel) and reviewed by an independent Data and Safety Monitoring Board (DSMB) overseeing the study and an Unblinded Senior Management Team from the sponsor. The DSMB, in accordance with its Charter, will make a recommendation to the study Sponsor on whether or not the study should continue according to the protocol or any modifications are needed based on the emerging benefit/risk profile.

After the review of the interim analysis results the Unblinded Senior Management Team will decide whether or not to proceed with regulatory submissions. This decision will be based on totality of the data including the overall consistency of the data and the benefit/risk assessment. If the Unblinded Senior Management Team decides to continue the study without regulatory submission, no additional personnel from the Sponsor will be unblinded to the interim data. Should the Unblinded Senior Management Team decide to proceed with regulatory submissions, an internal filing team will be unblinded to the interim data. The internal filing team will prepare and submit the marketing applications to the regulators. Members of both the Unblinded Senior Management Team and the internal filing team will not be involved with study management or operations after being unblinded to the interim data. All internal individuals who had access to the unblinded interim data will no longer be involved in the conduct of the blinded study.

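### At the interim, the LOCF sensitivity analysis enters earlier-visit scores as Month 15 scores for up to 59% of children, most of them not yet due, so it mixes visit effects and cannot show sensitivity to dropout

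*SAP*

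**What the plan says.** SAP 5.5.1.2 lists LOCF among the sensitivity analyses of the primary endpoint at the final analysis: "In the fourth sensitivity analysis the missing Month 15 values will be imputed by" carrying the last observation forward, in the ITT Set, with the main ANCOVA model. SAP 5.5.2.2 then extends it to the interim: "The sensitivity analyses planned for the final analysis of the primary endpoint will be repeated at the interim with the exception of the PPS analysis". In the table in 5.5.3, the interim column reads "ITT Set; last observation carried forward used to impute missing 15-month values". No rule separates children who have left the study from children who have not yet reached Month 15.

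On how much is missing at that point, SAP section 2 expects that "approximately 52 subjects will have attended the Month 15 assessment". It also says that, by then, "all 126 subjects will have had the opportunity to attend the assessment at Month 6". Under section 5.1 the interim may go ahead once "at least 39 subjects have completed the 15-month assessment". Section 5.5.2.1 acknowledges that "Endpoint values will not be available for many of the subjects at the interim analysis". Section 5.5.2.2 warns about small numbers for the completer analysis but gives no warning for LOCF.

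Elsewhere the SAP does draw the distinction:
- Section 3 defines the Interim Efficacy Set by whether a child could have been assessed at Month 15.
- Section 5.6.7 imputes no Month 15 milestone value for a child who qualifies for the Month 12 evaluable set but not for the Interim Efficacy Set.
- The fifth sensitivity analysis (5.5.3) overrides the multiple-imputation value only for discontinuation due to treatment failure or death.

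**The concern.** At the final analysis a missing Month 15 score means that the child dropped out or missed the visit, and LOCF asks how much the result depends on how such children are handled. At the interim most missing Month 15 scores belong to children still in follow-up. Carrying their scores forward changes what is being estimated: a Month 6, 9 or 12 score is analysed as if it were a Month 15 score. The footnote to the schedule of procedures allows the Day 274 assessments up to 7 days before dosing, so scores from Months 6 and 9 also precede the fourth dose or sham procedure.

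A gap between LOCF and multiple imputation at the interim therefore cannot be read as sensitivity to dropout. The sponsor's unblinded team will see these results when it decides on regulatory submission, and SAP 5.9 says of that choice: "This decision will be based on totality of the data including the overall consistency of the data". A lower LOCF estimate could be taken as inconsistency with the primary result when it only reflects the visits that were carried forward.

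**Working it through.** **The plan's own figure.** SAP section 9 claims at least 90% power for 70 versus 35 children, a 3-point difference, SD 4.4 and two-sided alpha 0.05. 3 / (4.4 × √(1/35 + 1/70)) = 3.29, and Φ(3.29 − 1.96) gives about 90.9% (90.4% from the noncentral t with 103 df). The claim reproduces. It serves here only as the source of the 3-point Month 15 effect.

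**Share carried forward.**
- Expected case (section 2): (126 − 52)/126 = 74/126 = 58.7%.
- At the minimum trigger (5.1): (126 − 39)/126 = 87/126 = 69.0%.

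Both are upper figures for children not yet due, because they include withdrawals and missed visits. The documents give no split.

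**What LOCF estimates.** With n15 children observed at Month 15 and the same mix of last visits in both arms:

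expected LOCF difference = (n15/126) × (Month 15 effect) + (1 − n15/126) × (mean effect at the visits carried forward)

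**Assumptions not in the documents.** These are the time course of the effect and the mix of last visits. I take last visits at Day 169, 274 or 365 (Months 6, 9, 12) and a true effect of 3 points at Day 456. Under linear growth the effect at day d is 3 × d/456, that is 1.11, 1.80 and 2.40 points at the three visits (mean 1.77).

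For n15 = 52 and linear growth:
- all carried from Month 6: 0.413 × 3 + 0.587 × 1.11 = 1.89
- equal mix: 0.413 × 3 + 0.587 × 1.77 = 2.28
- all carried from Month 12: 0.413 × 3 + 0.587 × 2.40 = 2.65

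| Assumed time course (3 points at Month 15) | All from Month 6 | Equal mix | All from Month 12 |
|---|---|---|---|
| Linear growth, 52 at Month 15 | 1.89 (63%) | 2.28 (76%) | 2.65 (88%) |
| Linear growth, 39 at Month 15 | 1.70 (57%) | 2.15 (72%) | 2.59 (86%) |
| Full effect by Month 6, 52 at Month 15 | 3.00 | 3.00 | 3.00 |
| Peak of 4 at Month 9, waning to 3, 52 at Month 15 | 2.69 (90%) | 3.19 (106%) | 3.29 (110%) |

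Percentages are of the true 3 points. In the last row the effects at the three visits are 2.47, 4.00 and 3.50.

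**Check by simulation.** In 4,000 simulated trials with 84:42 allocation, linear growth, an equal visit mix and assumed variance components, the ANCOVA gave a mean LOCF difference of 2.25, against 2.98 with full Month 15 data. This agrees with the formula.

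**The case against.** The strongest reply has four parts.

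**Direction.** A reader might infer that interim LOCF must understate the effect. The documents do not support that, because they give no time course. The last administration is on Day 274 and the endpoint is on Day 456, so neither a plateau nor some waning can be excluded. This part of the reply stands in full.

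**Value as a check.** A reader might infer that the analysis is worthless. That is too strong. If the effect grows, LOCF is pulled toward no difference, so a clearly positive LOCF result supports the primary finding; only a weak one is uninterpretable. It is also the one listed full-ITT interim analysis that does not predict unseen Month 15 scores from a model. The superseded original protocol even used the last observation at 6 to 15 months as the interim analysis itself. This is a reason to keep the analysis under an accurate label, not to present it as a Month 15 analysis.

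**Other information.** Section 5.5.2.2 also repeats the by-visit analyses of 5.5.1.3 at the interim, including mean change over time by arm and observed scores. Section 5.3 requires a summary of how much is missing. MMRM, completer and worst-value analyses accompany LOCF. A careful reader of the interim report could see whether the effect is still growing. This limits the harm considerably.

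**Use in decisions.** A reader might take 5.9 to mean that the DSMB will judge agreement across sensitivity analyses. It does not say so. Consistency is named only for the sponsor team's submission decision, the DSMB's recommendation is tied to benefit and risk, and neither sentence mentions sensitivity analyses. The risk of a false sign of inconsistency is an inference.

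None of this touches the central point, which needs no time course: the analysis as written does not target the Month 15 effect and cannot isolate dropout.

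**Conclusion.** The point holds as a minor defect of specification and labelling. Up to 74 of 126 interim Month 15 scores (58.7%) would be carried forward, most of them from children simply not yet due. It would be wrong to read all 74 as not yet due, since some may have withdrawn or missed the visit. Nor is every carried score sure to come from Month 6 or later: section 2 promises only the opportunity of a Month 6 visit, so a Day 92 score could be used.

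If the effect grows linearly to 3 points, the expected LOCF estimate is about 1.9 to 2.65, or 2.28 with an equal visit mix. If the effect is complete by Month 6 there is no bias. If it peaks and wanes the sign can reverse, depending on which visits are carried. These sizes illustrate assumed time courses and visit mixes and are not predictions for this trial. The primary interim test at 0.025 uses ANCOVA with multiple imputation and is not affected.

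**What to change.** In SAP 5.5.2.2 and the interim column of the 5.5.3 table, apply LOCF at the interim only to:
- children who died or withdrew before the clinical cut-off, whatever their date of first dose or sham procedure; and
- children whose Month 15 window (456 + 7 = 463 days) had closed without an assessment.

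For children still in follow-up, use their multiple-imputation values, as the fifth sensitivity analysis already does for scores missing for other reasons.

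The withdrawal rule should be written out. The Interim Efficacy Set cannot simply be borrowed as the filter, because it includes children who died or withdrew only if first dosed at least 449 days before cut-off, so later-enrolled withdrawals would fall outside it.

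If the present full-ITT version is kept for a look free of the imputation model, title it *last available visit* rather than Month 15, and add a caution like the one already given for the completer analysis.

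The cost is about one sentence and a data filter, with no change to the primary test or to alpha. The downside is that, when dropout is low, the restricted LOCF analysis will lie close to the primary analysis and add little.

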## 5.6 Analysis methods for the secondary endpoints

For many of the secondary endpoints, if a subject discontinues due to treatment failure or death then the subject will be defined to be a non-responder. This will be determined as described in Section 5.5.1.2

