## 8.9 Discontinuation of Study Treatment

A subject must permanently discontinue study treatment for any of the following:

- The subject's parents/guardians withdraw consent
- The subject experiences an adverse event that necessitates permanent discontinuation of study treatment

The reason for discontinuation of study treatment must be recorded in the Case Report Form (CRF) and source documentation.

Subjects that discontinue treatment will continue follow-up unless consent is withdrawn ([Appendix A](#)).

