### 5.6.1 Proportion of subjects who achieve a 3-point or greater increase from baseline in HFSME at 15 months

#### 5.6.1.1 Final analysis

##### *Main analysis*

The multiple imputation datasets produced for the analysis of the primary endpoint will be utilized. If a subject terminates the study prior to the 15-month assessment due to treatment failure or death, then the imputed value from the multiple imputation will be ignored and the subject will be considered a non-responder. Any subject in the ITT Set who has an increase from baseline HFMSE score of 3 or more points at Month 15 will be defined as a responder; otherwise, a subject will be considered a non-responder.

Treatment groups will be compared using logistic regression adjusting for each subject's age at screening and baseline HFSME score.

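### SAP 5.5.1.2 builds the treatment-failure list from treatment-termination reasons only, while the responder rules apply it to children who leave the study, so a failure who leaves after the last procedure may be missed

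*SAP*

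**What the plan says.** Four parts of the plan bear on who counts as a treatment failure.

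- **General rule, SAP 5.6.** For many secondary endpoints, "if a subject discontinues due to treatment failure or death then the subject will be defined to be a non-responder". The sentence does not say what is discontinued and does not require Month 15 to be missing. It adds: "This will be determined as described in Section 5.5.1.2".
- **Source of the list, SAP 5.5.1.2.** "The reasons for treatment termination are captured in the CRF in several categories", with a free-text field. None of the listed categories is lack of benefit. A blinded medical review before unblinding decides which cases are failures, and the resulting list determines response. The fifth sensitivity analysis of the primary endpoint uses it "for subjects who have a missing 15-month assessment and discontinue due to treatment failure or death".
- **Endpoint rules.** For the 3-point HFMSE responder (5.6.1.1) the trigger is leaving the study: "If a subject terminates the study prior to the 15-month assessment due to treatment failure or death", the imputed value is set aside and the child is a non-responder. SAP 5.6.2.1 (any new milestone) and 5.6.5.1 (standing alone, which 5.6.6 follows for assisted walking) have the same trigger. So does the worst-value sensitivity analysis for the Upper Limb Module in 5.6.4. SAP 5.6.7 refers instead to the reason why the Month 15 value is missing.
- **Stopping treatment is not leaving the study.** Protocol 8.9: "Subjects that discontinue treatment will continue follow-up unless consent is withdrawn". Protocol 8.10 separately requires the reason for study withdrawal on the CRF, and SAP 4.1 reports both sets of reasons.

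**The concern.** The list and the rule it serves describe different events. The list starts from the end of treatment; the rule starts from the end of study participation. They come apart after Day 274, when the last procedure has been given and about six months of follow-up remain. A child who completes every procedure and then leaves before Day 456 for lack of benefit is one whom 5.6.1.1 means to count as a non-responder. With no treatment termination on record, that child may never reach the reviewers. The Month 15 HFMSE is then multiply imputed and can earn part of a response.

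The 3-point responder rate is first in the order of secondary tests. Under SAP 5.2, if it is not significant, formal testing ends and the lower-ranked endpoints become exploratory. A list that misses eligible children also cannot be repaired blind once the data are unblinded.

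**Working it through.** **Plan's own figure.** SAP 9 states at least 90% power for a 3-point difference, SD 4.4, 70 against 35, two-sided 0.05. Noncentrality = 3 / (4.4 × √(1/35 + 1/70)) = 3.29, which gives power 0.909 (normal) or 0.904 (noncentral t, 103 df). The figure reproduces. The difference and SD are used below.

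**Length of the gap.** Day 274 to Day 456 is 182 days, out of 455 from Day 1: 182/455 = 40% of follow-up with no procedure left to stop.

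**Inputs for the size.**
- Group sizes 84 and 42 (SAP 5.1).
- Mean change 3 and SD 4.4 on drug: the design difference and SD, with an assumed sham mean change of 0. The same mean and SD are assumed at the last observed visit.
- SAP 5.3 imputes HFMSE by treatment group, using the child's baseline, age and all available later scores. This is approximated by a bivariate normal for the last observed change and the Month 15 change, with correlation ρ (assumed 0.5 to 0.9).
- Three missed drug-arm failures (assumed; the documents give no failure count).

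**Formula.** Given a last change L, the Month 15 change has mean 3 + ρ(L − 3) and SD 4.4√(1 − ρ²). The imputed responder probability p is the chance that it is at least 3. The rule intends 0, so the rise in the drug rate is 3p/84.

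| ρ | L = 0: p | rise (points) | L = −3: p | rise (points) |
|---|---|---|---|---|
| 0.5 | 0.347 | 1.24 | 0.216 | 0.77 |
| 0.7 | 0.252 | 0.90 | 0.091 | 0.33 |
| 0.8 | 0.182 | 0.65 | 0.035 | 0.13 |
| 0.9 | 0.080 | 0.29 | 0.002 | 0.01 |

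Example: ρ = 0.5, L = 0 gives mean 1.5 and SD 3.81; p = 1 − Φ(1.5/3.81) = 0.347; 3 × 0.347/84 = 1.24 points.

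**Ceiling.** If imputation ignored the child's own scores, p would be the drug-arm rate of 0.50, and the rise 3 × 0.50/84 = 1.8 points. At that ceiling one missed child is worth 0.50/84 = 0.60 points on drug and 0.248/42 = 0.59 on sham (0.248 = 1 − Φ(3/4.4)). Failures missed in both arms therefore largely offset in the difference, which is 50.0 − 24.8 = 25.2 points under these assumptions.

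**Other analyses that use the list.** In the third sensitivity analysis of 5.6.1, a missed failure is excluded instead of counted as a non-responder. In the worst-value analyses for HFMSE and Upper Limb, a missed failure keeps the imputed value instead of the worse of baseline and last observation.

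**Milestones.** Under SAP 5.6.2 a missing last visit takes the lowest value observed in the same age stratum and arm. That is failure unless every observed child there achieved the milestone, so being off the list normally changes nothing.

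**The case against.** The strongest reply is that the plan already works as intended. Three parts of it stand.

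*Observed responders are not overridden.* From the lead sentence of 5.6 a reader might infer that a child who stops treatment for failure, stays in follow-up and responds at Month 15 becomes a non-responder. The documents do not support that. SAP 5.6.3 and 5.6.4 use discontinuing and terminating the study interchangeably between text and summary table. Sections 5.6.1.1, 5.6.2.1 and 5.6.5.1 all require leaving the study before Month 15 and set aside imputed values only. The fifth sensitivity analysis in 5.5.1.2 requires a missing Month 15. The lead sentence is merely looser than the rules below it.

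*Missed failures are not imputed as typical of their arm.* The HFMSE imputation uses the child's own earlier scores, so a poor course lowers the imputed chance of response well below 0.50, as the table shows. Milestones take the lowest observed value.

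*The effect is partly bounded.* The second sensitivity analysis in 5.6.1 makes every missing Month 15 a non-response, and the fourth uses observed values only.

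It can also be said that the CRF is not in hand. Its categories include voluntary withdrawal and free text, and SAP 4.1 allows reasons of both kinds to be reclassified before lock. That is why the child may miss the list, not certainly will. But 4.1 concerns subject accounting, and 5.5.1.2 names only treatment termination as the source.

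**Conclusion.** The mismatch of source is real and minor. As written, the failure list can miss a child who completes all procedures and then leaves the study for failure, contrary to the rule in 5.6.1.1. The consequence is mainly confined to the rank 1 HFMSE responder endpoint, its third sensitivity analysis, and the worst-value analyses for HFMSE and Upper Limb. With three missed drug-arm failures and a last change of 0, the drug responder rate rises by about 0.3 to 1.2 points; a worse last change gives less. The failure count, the sham mean change, the equal mean and SD at the last visit and the correlations are all assumptions. It is worth correcting because the affected endpoint gates the hierarchy and the adjudication must be settled blind, not because the shift is large.

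**What to change.** In SAP 5.5.1.2, base the blinded adjudication on the study-withdrawal reasons and their free text as well as the treatment-termination reasons. Then align the lead sentence of 5.6 and the summary tables with the endpoint sections, and use the same trigger in 5.6.7: a child whose Month 15 assessment is missing because the child left the study for treatment failure, or died, is a non-responder; an observed Month 15 value stands.

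The cost is a few sentences of SAP text and a slightly wider blinded review before unblinding. Both sets of reasons are already collected, so no new data are needed.
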